All adverse events will be graded as follows in their relation to IFER: definitely not related, unlikely to be related, possibly related, definitely related or insufficient information. All cases rated as possibly or definitely related will be defined as an SAE. These SAEs will be reported to the University of Michigan Sponsor-Investigator within 48 hours. The site PI will be contacted immediately and the case will be evaluated for reporting to IRB, FDA and study termination, if deemed necessary. Each clinical site will report SAEs to their local IRB as per their standard reporting policy. As per 21 CFR 312.32(c), the sponsors will also notify FDA and all participating investigators in an IND safety report of any adverse experience associated with the use of the drug that is both serious and unexpected.

Data Safety Monitoring Board

An independent data safety monitoring committee will be established to monitor the study for safety and to determine if a statistical difference has been achieved between the two groups for the primary outcome measure at interim data analyses. The data safety monitoring committee will review the data at the halfway point of the study to assess the safety and efficacy of the study to that point. If safety issues are revealed the study investigators and each site's IRB will be notified immediately. The data safety monitoring committee will also ensure that adverse events are promptly reported to the FDA, and all participating investigators will be notified as well of any adverse experience associated with the use of the drug that is both serious and unexpected.

Sample Size Determination

The sample size was calculated for the primary outcome (rate of rise of direct bilirubin) using previously published data as well as our clinical experience.^{22,23} We have assumed that the mean bilirubin levels at baseline, 4 weeks, 8 weeks and 12 weeks in the standard dosing group (2-3 g/kg/day) will be 0.55 mg/dL, 1 mg/dL, 1.5 mg/dL and 2 mg/dL corresponding to a slope of 0.125 mg/dL/week over 12 weeks. The standard deviation of the bilirubin measures at each of these four time points is 1. Likewise, we have estimated that the mean bilirubin levels at baseline, 4 weeks, 8 weeks and 12 weeks in the minimization group (1 g/kg/day) will be 0.45 mg/dL, 0.5 mg/dL, 0.45 mg/dL and 0.5 mg/dL (a slope of roughly zero). The standard deviation of the bilirubin measurements at

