each of these four time points is 1. The correlation of any two adjacent measures on the same individual is 0.5. This correlation drops to 0.354 between baseline and 8 weeks and to 0.25 between baseline and 12 weeks.

Using the above assumptions, a sample size of 15 subjects per group using a repeated measures ANOVA will have 85% power to detect the change in slopes as being significant at the 0.05 level, 79% power to detect a difference in means overall between groups and 88% power to detect the general change in means over time across the two groups. When the sample size is increased to 20 subjects per group, the above power numbers increase to 95%, 90% and 96%, respectively. If 30 subjects are recruited per group this design will allow for a 33% attrition rate by twelve weeks as we expect that not all patients will require PN for the full 12 weeks of the initial study period. Thus, we will recruit a minimum of 30 subjects per group to ensure adequate power to detect our primary outcome measure.

Of the secondary outcomes, sample size was also calculated for the incidence of cholestasis. Assuming an incidence of 50% in the standard group and an incidence of 10% in the minimization group, with $\alpha = 0.05$ and power of 80%, a sample size of 23 is required for each group. Regarding the other secondary outcomes, our sample size is large enough to allow for establishing trends which may then highlight avenues for future research.

Planned Statistical Analysis

All data analysis will be directed and performed by a statistician through the Center for Statistical Consultation and Research at the University of Michigan (<http://cscar.research.umich.edu/about/>). Data will be analyzed using SAS software release 9.3 for Windows (Copyright, SAS Institute Inc., SAS and all other SAS Institute Inc. product of service names are registered trademarks or trademarks of SAS Institute Inc., Cary, NC, USA). All study subjects will be included in the statistical analysis in an intent-to-treat manner.

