Descriptive statistics using standard statistical tests (e.g. Student's t-test, paired sample t-test, Wilcoxon rank sums tests, Fisher's exact tests, Chi-square test, McNemar's test, etc.) will be used throughout the statistical analysis of data. Logistic regression will be used to compare differences between groups. Because septicemia can exacerbate PNAC, we will include the incidence of septicemia as a covariate in our analysis. Septic episodes will be defined as positive cultures or clinical presentation consistent with sepsis during the 7 day period corresponding to the subject's weekly bilirubin value. The number of septic episodes will be accounted for using a Poisson regression analysis (or possibly a negative binomial regression if there is more variability than expected for a Poisson distribution), with the total time on PN as an offset, allowing us to compare the rate of occurrence of septic episodes in the two groups.

Primary Outcome Measure

The primary outcome measure – change in direct bilirubin as a function of time (mg/dL/week) between the two groups – will be evaluated using a linear mixed model analysis to compare the slope of total bilirubin levels between the standard and reduced groups. This model will allow us to examine the degree of variability between subjects in the rate of change over time, and will take this variability into account in the model by including a random effect for the slope of time for each subject as well as a random intercept for each subject.

Secondary Outcome Measures

1. Time to PNAC (direct bilirubin ≥ 2 mg/dL) and time to severe PNAC (direct bilirubin ≥ 4 mg/dL)

The time to development of a first occurrence of PNAC and of severe PNAC will be evaluated using survival analysis. Initially, we will compare the two groups using Kaplan-Meier curves, but the eventual analysis will take into account important covariates, such as development of sepsis, average IVFE dose and percentage of calories from enteral feeds using a Cox proportional hazards survival analysis. We will test whether the proportional hazards assumption is met for the analysis by including an interaction term between treatment group and time to see if any differences between the groups are consistent or increase/decrease over time. The effect of important time-varying covariates (e.g., septic episodes) can also be taken into account using a Cox model.

2. Level of peak total and direct bilirubin

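### An interim efficacy test of the primary outcome is planned with no interim significance level, no adjusted final level and no stated action if it is positive

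*Combined protocol and SAP*

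**What the plan says.** The Data Safety Monitoring Board section gives the committee a safety role and a second task: "to determine if a statistical difference has been achieved between the two groups for the primary outcome measure at interim data analyses". The next sentence says that it "will review the data at the halfway point of the study to assess the safety and efficacy of the study to that point". One review is therefore described. The plural in the first sentence leaves it unclear whether that is the only one. Halfway is not defined: it could mean recruitment, completed 12-week follow-up or calendar time.

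The section states a consequence for one kind of finding only. It begins "If safety issues are revealed the study investigators", and goes on to require notice to the investigators and the sites' IRBs. No sentence says what follows a positive efficacy finding.

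Under Sample Size Determination, 15 infants per group "will have 85% power to detect the change in slopes as being significant at the 0.05 level". This is the only level given for this outcome. The target of 30 per group is set because "this design will allow for a 33% attrition rate by twelve weeks".

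Under Primary Outcome Measure, the outcome "will be evaluated using a linear mixed model analysis to compare the slope" between arms. No level is given there, and none of the analysis sections mentions an adjustment for an interim look.

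**The concern.** The committee is asked for a statistical finding on the primary outcome before the trial is complete. Such a finding needs a criterion, and the only one in the document is 0.05. If the committee applies that level, and the result can end the trial or be reported as its answer, the primary hypothesis has two chances to reach 0.05 and the overall false-positive rate exceeds 0.05.

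There is also a practical gap. If the planning assumptions are right, a nominally significant halfway result is likely. With no rule in place, the decision to stop, continue or disclose would be made after seeing the data. Stopping early would also shrink the sample for growth, safety and the 12- and 24-month neurodevelopmental assessments.

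**Working it through.** **Inputs (Sample Size Determination).** Mean bilirubin at weeks 0, 4, 8 and 12: 0.55, 1, 1.5, 2 mg/dL (standard) and 0.45, 0.5, 0.45, 0.5 mg/dL (reduced). SD 1 at each time. Correlations 0.5 (adjacent), 0.354 (two steps) and 0.25 (three steps). Level 0.05, taken as two-sided because sidedness is not stated. Recruitment is 30 per group with 33% attrition, so 30 × 0.67 = 20.1, about 20 completing. Half of recruitment is 15 per arm; after the same attrition 15 × 0.67 = 10.05, about 10.

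**Step 1. Reproduce the plan's power.** Simulating the uncorrected repeated measures ANOVA group-by-time test at a single 0.05 level (100,000 trials) gives 84.6% with 15 per group (stated 85%) and 93.5% with 20 (stated 95%). The stated power therefore corresponds to one full-level test, with no alpha set aside for an interim look.

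**Step 2. Slope contrast on the same inputs.** The least-squares weights for the four visits are (−6, −2, 2, 6)/80 per week.

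- Arm differences in means: 0.10, 0.50, 1.05, 1.50.
- Slope difference: (−0.6 − 1.0 + 2.1 + 9.0)/80 = 9.5/80 = 0.11875 mg/dL/week.
- Variance of one infant's slope: [80 + 2(6 − 4.248 − 9 − 2 − 4.248 + 6)]/6400 = 65.008/6400, so SD = 0.1008.
- Standardised difference: 0.11875/0.1008 = 1.178.
- Power from the noncentral t with 2n − 2 degrees of freedom and noncentrality 1.178 × √(n/2).

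**Step 3. Chance that a halfway test at 0.05 is significant if the planning assumptions hold.**

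| Complete infants per arm | Slope contrast | ANOVA group-by-time (simulated) | Plan's figure |
|---|---|---|---|
| 15 (no attrition) | 87.6% | 84.6% | 85% |
| 10 (33% attrition) | 70.3% | 66.6% | not given |

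The slope contrast runs a few points above the plan's ANOVA, so I use the plan's 85% for 15 per arm and about 66% to 70% for 10. Both rows use infants with complete 12-week data. If many of the recruited half have not reached week 12, the chance is lower: 59% with 8 complete infants per arm and 38% with 5 (slope contrast). The planned mixed model would also use partial follow-up, which would raise these figures. The dose change that the protocol triggers on direct bilirubin is not modelled.

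**Step 4. Type I error if a significant result at either analysis counts.** Under the null, the interim and final Z statistics are bivariate normal with correlation √f, where f is the information fraction at the look. Overall error = 1 − P(|Z₁| < 1.96 and |Z₂| < 1.96).

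| f | Overall type I error |
|---|---|
| 0.25 | 0.091 |
| 0.50 | 0.083 |
| 0.75 | 0.073 |

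The range is an assumption, because halfway is undefined. If the interim result can never stop the trial or be declared positive, only the final test matters and the error is 0.050.

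**Step 5. A boundary that holds 0.05.** O'Brien-Fleming with one look at f = 0.50 uses critical values c/√f. Solving for overall error 0.05 gives c = 1.977, hence 1.977 × √2 = 2.797 at the interim (p < 0.0052) and 1.977 at the end (p < 0.048). Final-test power for the slope contrast with 20 per arm is 95.3% at 0.05 and 95.1% at 0.048.

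**The case against.** The best counter-argument is that no sentence lets a positive interim result stop the trial or count as its conclusion. The mention of study termination just before the monitoring section concerns serious adverse events, and the sample-size section commits to at least 30 infants per group. On that reading recruitment continues, the final test stands alone and the error is 0.050. This is a fair reading and it stands as one possibility. It is not secure, because the committee's stated task is to establish whether a difference has been reached, and the plan does not say that such a finding has no effect.

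A reader might infer that the trial's type I error is 0.083. The documents do not support that: the figure depends on a use of the interim result that they neither permit nor rule out.

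A reader might also infer several unadjusted efficacy looks, with a larger inflation. Only one review is described, and a further look rests on a plural noun alone.

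The details might sit in a committee charter, but the documents cite none.

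**Conclusion.** The gap is real and touches the primary inference. One halfway efficacy review is described; whether it is the only look is unclear, and its level, the final level and the action on a positive result are all absent. Control of type I error at 0.05 is therefore not shown. The error is 0.050 if only the final test counts and about 0.083 if a halfway result at two-sided 0.05 can also count, with the second figure resting on one look at half the information. The likelihood of a significant halfway result rests on the plan's own means, SD and correlations, and on enough infants having completed 12 weeks by then. The plan should be corrected, and the correction is small.

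**What to change.** Before any interim data are seen, choose one of the following.

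**(a) Safety-only review.** State that the interim review covers safety only and that the primary outcome is tested once, at the end, at 0.05. Remove the efficacy determination from the committee's tasks. This suffices on its own and costs no power, but gives up an early efficacy answer.

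**(b) One defined efficacy look.** State that there is one efficacy look. Define halfway. Name an alpha-controlling boundary computed at the actual information fraction, give the adjusted final level, and say what follows if the boundary is crossed, including whether recruitment continues. O'Brien-Fleming at 50% information (p < 0.0052, then p < 0.048) is one example; other alpha-controlling boundaries would also do. The cost is 0.2 percentage points of final-test power at 20 per arm.

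Under (b), first reconcile the Primary Outcome Measure paragraph. It defines the outcome as change in direct bilirubin but has the model compare slopes of total bilirubin. The interim and final tests must use the same outcome.

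Either option takes a few sentences in the monitoring and analysis sections and no additional infants.

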This is a multi-institution, prospective, randomized study evaluating IVFE dose reduction on the development of PNAC as a proxy measure of PNALD in neonates requiring prolonged PN. The definition of PNAC will be that used predominantly in the literature – a direct bilirubin level of ≥ 2 mg/dL, documented on two occasions 1 week apart, in patients who have required parenteral nutrition for more than 2 weeks. **Eligible neonates will be randomized into two treatment arms: standard IVFE administration (3 g/kg/day) or IVFE reduction (IFER) (1 g/kg/day).** A total of 60 subjects (30 subjects per arm) will be included in the study. The study will evaluate

short- and long-term outcomes of this strategy. In the short-term, infants will be followed for up to 12 weeks for the development of PNAC. If a subject's PN is discontinued before 12 weeks, and if they remain in the hospital, follow-up data will be collected for an additional 7 days but not beyond a total of 84 days. Only standard-of-care data will be collected during these 7 days. No procedures will be performed for the purpose of this study during these 7 days. In the long-term, subjects' neurodevelopmental outcomes will be assessed at 12 and 24 months corrected gestational age (± 2 weeks).

Primary outcome measure:

1. The rate of rise of direct bilirubin as a function of time (mg/dL/week) between the two groups over 12 weeks or until the subject has been off of PN for >7 days, whichever comes first.

Secondary outcome measures

1. Initial 12 week period:
 - a. The incidence of PNAC (direct bilirubin ≥ 2 mg/dL) and severe PNAC (direct bilirubin ≥ 4 mg/dL in subjects on parenteral nutrition for at least 2 weeks)
 - b. The time to development of PNAC and severe PNAC
 - c. The peak total and direct bilirubin levels
 - d. The incidence of EFAD
 - e. Adequacy of growth as evaluated by z-scores for weight, height, and head circumference
 - f. Other safety measures assessed during the initial 12 week period will include adverse events (e.g., episodes of sepsis and catheter-related blood stream infections).
2. Long-term follow-up:

Neurodevelopmental assessments will include:

 - a. At 12 months corrected gestational age (± 2 weeks):
 - i. Bayley Scales for Infant and Toddler Development (BSID-III)
 - b. At 24 months corrected gestational age (± 2 weeks):
 - i. Bayley Scales for Infant and Toddler Development (BSID-III)
 - ii. MacArthur-Bates Communicative Development Inventories (CDI)

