4. Necrotizing enterocolitis requiring surgical intervention (drain placement, laparotomy, bowel resection)
5. Volvulus
6. Intestinal atresia with >50% bowel loss as defined by bowel length nomogram (**Figure 1**)

[figure not shown]

Figure 1. Nomogram estimating normal small bowel length based on height at the time of surgery.²⁶

This population was selected because of their high risk for developing PNAC due to their underlying disease process and limited ability to tolerate enteral feeds. Using this group of subjects will allow for sufficient data to be obtained with the fewest number of subjects over the shortest period of time.

No preference will be given to sex, race or ethnic background during the enrollment of subjects into the study.

Exclusion Criteria

1. Birthweight <1kg
2. A metabolic pathway defect which is associated with liver dysfunction in the neonatal period including: hereditary fructose intolerance, galactosemia due to transferase deficiency and neonatal tyrosinemia, and/or disorders of lipid metabolism
3. A history of hepatic insufficiency as defined by either a biopsy with cirrhosis and/or a marked aberration in synthetic function (defined by elevated prothrombin time (INR ≥ 2.0) with no evidence of a systemic coagulopathy and no administration of an anticoagulant)
4. Primary or secondary liver disease, including hepatitis, as defined by either an elevated prothrombin time (INR ≥ 2.0) or elevation of liver function tests (AST and ALT) greater than twice the upper limit of the age-adjusted norm
5. Congenital obstruction of the hepatobiliary tree (e.g. biliary atresia, choledochal cyst)
6. History of PNAC or a direct bilirubin >2 mg/dL at any time prior to enrollment/randomization
7. Renal failure (as defined by a creatinine >1.5 mg/dL)
8. Use of extracorporeal membrane oxygenation (ECMO), as hemolysis from the ECMO circuit may cause a mixed hyperbilirubinemia unrelated to the development of PNAC
9. Documented active infection which may be communicable, including infectious hepatitis or human immunodeficiency virus
10. Previous receipt of choleretic agents (e.g. ursodiol, phenobarbital, cholecystikinin). This is done in order to avoid the use of an agent which may reduce cholestasis and the development of PNAC.
11. Current administration of phenobarbital or other barbiturates
12. No infant with a congenital or acquired anomaly which will require major cardiovascular surgery
13. Major congenital or chromosomal anomaly

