Subject's family members, the statistical team and those administering the neurodevelopmental tests will be blinded to treatment assignment. Blinding of families and those evaluating neurodevelopmental outcomes is particularly important as these are subjective assessments which we do not want to be biased by the treatment assignment. Adequacy of blinding will be assessed at the end of the initial 12 week treatment period by asking parents which treatment arm they believe the subject has been assigned to. Assessment of the adequacy of blinding will be performed and changes made if blinding of parents is deemed to be suboptimal. It is not possible to blind the inpatient care team and the investigators as the remainder of the PN formulation (dextrose, protein) must be adjusted to deliver adequate caloric needs to the subjects based on their IVFE treatment assignment. The lack of blinding during this phase of the study will not influence the short-term outcomes as they are discrete measurements that cannot be biased by subjectivity.

Standardization of Parenteral Nutrition Across Study Centers

The following guidelines for parenteral nutrition administration have been established to provide uniformity among study sites. Each site will follow these guidelines.

Energy

Total caloric delivery will range between 100-120 Kcal/kg/day when PN is the only source of calories
Total non-protein caloric delivery will not exceed 100 Kcal/kg/day when PN is the only source of calories

Carbohydrate

Dextrose infusion rate (DIR) will be increased in the following manner, provided there is no aberration in the serum glucose levels:

Day 1	DIR 4-8 mg/kg/min
Day 2 and beyond	Advancement of DIR by 1-2 mg/kg/min per day to a goal of 11-18 mg/kg/min

	For study subjects 0-30 days old the maximum DIR will be 16 mg/kg/min For study subjects >30 days old the maximum DIR will be 18 mg/kg/min
--	---

If hyperglycemia develops (defined as serum glucose >150 mg/dL), subjects will be managed in accordance with standard guidelines²⁸

1. Confirmatory point of care glucose test performed
2. If confirmatory glucose >150 mg/dL, the DIR will be reduced daily in increments of 1-2 mg/kg/min as tolerated until the serum glucose normalizes
3. Insulin will only be administered if hyperglycemia has not been controlled by adjusting the DIR

Protein

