3. Weight, gestational age at the time of enrollment/randomization, and weekly thereafter
4. Inclusion diagnosis
5. Number of septic episodes according to standard definitions³⁸
6. Use of choleric medications
 - a. Ursodiol
 - b. Cholecystokinin
 - c. Phenobarbital
7. Nutritional data
 - a. Parenteral nutrition data
 - i. IVFE dose
 - ii. Dextrose infusion rate
 - iii. Total calories and % calories obtained via PN
 - b. Enteral nutrition data
 - i. Total calories and % calories being obtained via enteral route
 - ii. % calories obtained via breast milk
8. Growth parameters (whenever possible, obtain all growth measurements on the same day of the week)
 - i. Weight (with z-score) weekly (every 7 days ± 2 days)
 - ii. Height (with z-score) weekly (every 7 days ± 2 days)
 - iii. Head circumference (with z-score) weekly (every 7 days ± 2 days)
9. Additional safety data to be obtained from human subjects is summarized below, indicating any key differences in frequency of monitoring between the two groups:

Laboratory Parameter	Frequency (+24 hours)*
Fractionated bilirubin panel (includes total, indirect, and direct bilirubin)	One time weekly (Monday)
Serum bile acids (total)	One time monthly (every 4 th Monday on treatment)

Point of care or serum glucose measures	- Daily for the first 5 days of PN, then twice weekly (Monday, Thursday) - Confirmatory test if serum glucose is >150 mg/dL on electrolyte panel
Serum Triglycerides	One time weekly (Monday)
Essential Fatty Acid Profile	IFER Group: Every 2 weeks (Thursday) Standard Group: At the time of restriction of IVFE to 1 g/kg/day three days per week, then every 2 weeks (Thursday)
Comprehensive metabolic panel	Twice weekly (Monday, Thursday)
Magnesium level	Twice weekly (Monday, Thursday)
Phosphorus level	Twice weekly (Monday, Thursday)
Complete blood count	One time weekly (Monday)

* Lab draw volumes will be below each institution's daily limits

Definition of Sepsis

Sepsis will be defined in a standard manner using the following criteria (**Table 2**):³⁸

The presence of at least two of the following four criteria ***in the presence of or as a result of suspected or proven infection***:

1. Core temperature of >38.5C or <36C

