We recognize that neurodevelopmental outcomes may be influenced by other factors that extend beyond early interventions during the neonatal and infant periods. Such factors may include duration of parenteral nutrition, duration of IFER, mean IVFE dose, percent nutrition obtained via the enteral route compared to the parenteral route, type of enteral intake (i.e. breast milk), the development of essential fatty acid deficiency, as well as early intervention programs, attendance at daycare/preschool, and socioeconomic status. As such, we will evaluate study subjects every 6 months (\pm 30 days) and collect the following data, which will be used in final statistical analyses to evaluate predictive variables on neurodevelopmental outcomes:

1. Current parenteral and enteral nutrition parameters
2. Current IVFE dose/mean IVFE dose over course of previous 6 months
3. Essential fatty acid profiles (if available, according to each institution's standard of care), evaluating for development of essential fatty acid deficiency
4. Attendance at early intervention programs and/or daycare/preschool

Monitoring for Adverse Events

The study coordinator and investigators at each site will monitor for adverse reactions. Although generally very well-tolerated, the administration of PN with Intralipid® 20% is associated with a number of adverse events.

Determination of Expectedness:

Adverse events will be classified as expected or unexpected. Expected adverse events include those listed in the clinical protocol, the package insert for PN with Intralipid® 20%, and those events listed in the informed consent document.

These may include, but are not limited to:

1. Line complications including:
 - a. Catheter-related blood stream infection (CRBSI)
 - i. Defined as: A laboratory-confirmed bloodstream infection (LCBI) where central line (CL) or umbilical catheter (UC) was in place for >2 calendar days on the date of event, with day of device placement being Day 1, *and* a CL or UC was in place on the date of event or the day before. If a CL or UC was in place for >2 calendar days and then removed, the LCBI criteria must be fully met on the day of discontinuation or the next day^{51,52}
 - ii. This is in distinction to a catheter-related blood stream infection (CRBSI) whose definition requires removal of the catheter⁵¹
 - b. Need for catheter replacement
2. Hyperglycemia > 300 mg/dL
3. Hypertriglyceridemia >400 mg/dL
4. Development of essential fatty acid deficiency

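### Sepsis is collected under one definition and analysed under a different one, and neither limits the between-arm rate to episodes that begin after randomisation

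*Combined protocol and SAP*

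**What the plan says.** Secondary outcome 1f lists, among other safety measures, "adverse events (e.g., episodes of sepsis and catheter-related blood stream infections". Sepsis then receives two descriptions.

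- **Collection.** Data Collection item 5 asks sites for the number of septic episodes by standard definitions and cites reference 38. The Definition of Sepsis section cites the same reference and requires "The presence of at least two of the following four criteria" (temperature, heart rate, respiratory rate or ventilation, leukocytes) "in the presence of or as a result of suspected or proven infection".
- **Analysis.** The Planned Statistical Analysis says: "Septic episodes will be defined as positive cultures or clinical presentation consistent with sepsis during the 7 day period" matched to the subject's weekly bilirubin. The episode count goes into a Poisson or negative binomial model with total PN time as offset, to compare the arms. Sepsis is also a covariate in the analyses of PNAC. Under Potential Confounding Variables, sepsis is named again as a secondary outcome.

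On infection at entry, the Inclusion Criteria list meconium ileus and peritonitis (item 1) and "Necrotizing enterocolitis requiring surgical intervention (drain placement, laparotomy, bowel resection" (item 4). The only infection exclusion (Exclusion Criteria item 9) covers active infection that may be communicable. Adverse events are recorded from consent, and randomisation follows consent.

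On blinding, the plan says the inpatient team and the investigators cannot be blinded, and adds: "The lack of blinding during this phase of the study will not influence the short-term outcomes".

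**The concern.** The variable that sites are told to record is not the one the statistician is told to analyse, and no text says which governs. The analysis wording gives no criteria for its clinical component, and the people applying it know the arm. The plan accepts open treatment on the ground that the short-term outcomes are objective measurements, and this component does not fit that ground.

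Separately, an infant with peritonitis or surgical necrotising enterocolitis may meet either description of sepsis at randomisation. Without a new-onset rule, that illness can enter the between-arm rate although the assigned lipid dose cannot have caused it. At stake are the interpretation of the sepsis comparison and, through the covariate, the adjusted PNAC results.

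**Working it through.** **1. The two descriptions, case by case**

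| Case | Definition of Sepsis (collected) | Planned Statistical Analysis (analysed) |
|---|---|---|
| Positive culture, two or more signs | Sepsis | Septic episode |
| Positive culture, no sign or one sign | Not sepsis | Septic episode |
| No positive culture, infection suspected, two or more signs | Sepsis | Depends on the judgement of clinical presentation |
| No positive culture, infection suspected, one sign | Not sepsis | Depends on the same judgement |

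The second row is a definite disagreement. The last two cannot be settled from the text.

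**2. Entry infection**

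Neither sepsis text contains a baseline, washout or onset-after-randomisation condition. Two of the six inclusion diagnoses can carry abdominal infection, and the communicable-infection exclusion does not name it. Determination of Relatedness lets the site investigator leave usual effects of the condition unrecorded as adverse events. Its examples (emesis, reflux, procedural pain) do not include infection, and the decision is discretionary and unblinded, so it does not replace an onset rule.

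**3. Direction and size of the dilution**

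The documents give no infection rate, so there is no stated figure to reproduce. All inputs in this step are assumptions: 0.75 and 0.50 new episodes per infant in the two arms, equal PN time, and an entry episode in a share *e* of infants, the same in both arms.

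Observed ratio = (0.75 + e) / (0.50 + e)

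| e | Observed ratio | ln(observed) / ln(1.50) |
|---|---|---|
| 0 | 0.75/0.50 = 1.50 | 1.00 |
| 0.15 | 0.90/0.65 = 1.38 | 0.80 |
| 0.30 | 1.05/0.80 = 1.31 | 0.67 |
| 0.40 | 1.15/0.90 = 1.28 | 0.60 |

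The log ratio shrinks by about 20% to 40%. The difference is (0.75 + e) − (0.50 + e) = 0.25 for every e.

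**4. What this means with 30 per arm**

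Power is for a two-sided 0.05 Wald test on the log rate ratio with Poisson variance, se = √[1/(30μ₀) + 1/(30μ₁)]. The lower-rate arm has an assumed 0.5 new episodes per infant.

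- True ratio 1.5: se = √(1/15 + 1/22.5) = 0.333 and power is 23%. Adding 0.1, 0.3 or 0.5 entry episodes per infant gives ratios of 1.42, 1.31 and 1.25, with power of 20%, 17% and 15%.
- True ratio 2.0: power is 59%. The same additions give ratios of 1.83, 1.62 and 1.50, with power of 54%, 47% and 41%.

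Power for a ratio of 1.5 is low even without dilution, so the loss matters more for the estimate than for the test.

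**The case against.** The strongest reply is that the analysis wording may be shorthand for the term already defined, with its 7-day window serving only to link sepsis to the weekly bilirubin. The link is a fair reading and a reason to keep the window for the covariate. It does not explain why a positive culture alone suffices, and the same definition feeds the arm comparison.

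It is also true that the collected definition admits suspected infection, which the same unblinded team judges. Adopting it narrows the room for judgement without removing it. The plan further says that its size only allows trends in the other secondary outcomes, and outcome 1f names sepsis only as an example of an adverse event. That limits the weight of the point but does not reconcile the definitions.

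A reader might infer more than the documents support:

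- **That catheter-related infection also has two definitions.** It has one operative definition, a laboratory-confirmed bloodstream infection with a line in place for more than two calendar days. A note follows: "This is in distinction to a catheter-related blood stream infection (CRBSI) whose definition requires removal of the catheter". That is a contradictory label without a second counting rule. The day rule removes the earliest events. Whether the laboratory criteria exclude infection secondary to another source rests on cited documents that are not available here.
- **That the arm comparison depends on which text a site follows.** The conflict is between collection and analysis. Randomisation is equal within centre, so a site's choice of text would not by itself bias the comparison.
- **That a three-week illness counts once under one text and three times under the other.** Neither text says how episodes are separated.
- **That every defect pulls toward no difference.** Only arm-neutral entry infection does so, on the ratio scale. Repeat counting that is equal across arms leaves the expected ratio unchanged, and unblinded judgement could move it either way.

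**Conclusion.** The concern holds for sepsis. The collected and analysed definitions are not equivalent. The analysed one has an unspecified clinical component judged without blinding, and neither confines the between-arm rate to new episodes. The direction of the entry-infection effect on the rate ratio is clear if such episodes are counted equally in both arms. Its size is unknown: the fall from 1.50 to between 1.38 and 1.28 rests wholly on assumed rates and an assumed entry share of 15% to 40%. The line-infection label is an editorial matter. This should be corrected because it changes what is counted and costs little, but nothing here shows that the sepsis comparison is biased in a known amount.

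**What to change.** 1. **Safety comparison.** In the Planned Statistical Analysis, define the septic episode for the between-arm rate by the two-of-four criteria in Definition of Sepsis. Count only episodes with onset after randomisation that are distinct from the entry illness, one count per illness. Report culture-proven episodes separately as the more objective component.
2. **Covariate.** Keep sepsis in the bilirubin and PNAC models as a separate variable. Use the same criteria, keep the link to the 7-day bilirubin window, and include entry and persisting sepsis, because the plan itself says that sepsis may raise direct bilirubin. Applying the new-onset rule here would remove adjustment that the plan intends.
3. **Editorial.** In outcome 1f and Determination of Expectedness, name the line-infection outcome as the laboratory-confirmed, central-line-associated bloodstream infection it measures.

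The cost is wording in three places and an onset date on the existing form. Fewer episodes will be counted in the safety comparison, and someone must judge whether an episode is distinct from the entry illness. No treatment rule changes.
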